#### 5.1.2 Baseline and fully adjusted analyses

We will also perform baseline and fully adjusted analyses with covariates for each outcome. First, we will perform bivariate analyses using the likelihood ratio test to test the association between the covariates with each outcome. Covariates with a p-value < 0.1 will be included in the adjusted analysis. Covariates with little variation in the study population (e.g., prevalence < 5%) will be

excluded. We will also evaluate the collinearity between potential covariates using the Variance Inflation Factor.

Potential covariates are listed below:

- Child sex: female or male
- Birth order: first-born or  $\geq$  second-born
- Municipality economic status: High or low
- Maternal height in centimeters
- Maternal pre-pregnancy BMI: BMI in  $\text{kg}/\text{m}^2$
- Maternal hemoglobin level at baseline in  $\text{g}/\text{L}$
- Maternal history of hypertension at baseline: With or without any history of hypertension
- Maternal age in years
- Maternal education: no education/incomplete primary/unknown, completed primary (6 years of formal education), completed secondary (9 years of formal education), completed greater than secondary
- Number of children under 5 yo in the household
- Number of household members
- Maternal marital status: monogamous marriage, polygamous marriage, or unmarried [single, divorced, widowed]
- Maternal occupation: housewife or working mother
- Paternal occupation: non-private sector and unemployed or private sector
- Monthly household expenditure in Indonesian Rupiah per month
- HOME inventory score (home environment)
- Screen time per day in minutes
- Staff members performing the assessment (for Bayley-III)

Two versions of adjusted analyses will be conducted as described below.

- Baseline adjusted model: This model will include covariates in minimally adjusted model and any of the following baseline covariates that are significantly associated at  $p < 0.1$  with the outcomes: child sex, birth order, maternal height, maternal pre-pregnancy BMI, maternal hemoglobin, maternal age, paternal age, paternal education, number of children under 5 yo in the household, number of household members, maternal marital status, maternal occupation, paternal occupation, household expenditure.
- Fully adjusted model: Then, we will adjust for any covariates collected at follow-up (HOME inventory score, screen time) that are significantly associated at  $p < 0.1$  with the outcomes. For any covariates collected after baseline, we will check whether any differences are based on allocation groups at  $p < 0.1$ . Significant differences indicate potential mediators. Therefore, we will exclude them from the model.

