### 2.7.2 Bayley Scales of Infant and Toddler Development, 3rd edition (Bayley-III)

Two trained psychologists conducted the Bayley-III assessment in a room with minimal distractions. The subscales included in this analysis were cognitive, receptive language, expressive language, fine motor, and gross motor. Before administering the assessment to study participants, we evaluated inter-rater agreement between the two assessors using data from three children, which resulted in a 56% agreement rate—considered moderate. Following this result, a group discussion was held to address the areas of disagreement. Due to pandemic-related constraints and time limitations, we were unable to conduct additional inter-rater reliability assessments.

The Bayley-III assessments were conducted twice between 4 and 6 months of age. For this analysis, we will use the first assessment for each child as the outcome measure to avoid potential influence from prior exposure to the Bayley-III assessment within a short interval. The outcomes derived from this assessment include:

- Bayley-III *Cognitive score*: Z-score converted raw score of Bayley-III cognitive subscale (continuous).
- Bayley-III *Cognitive composite score*: Score based on conversion of Bayley-III cognitive scaled score (continuous).
- Bayley-III *Receptive language score*: Z-score converted raw score of Bayley-III receptive language subscale (continuous).
- Bayley-III *Expressive language score*: Z-score converted raw score of Bayley-III expressive language subscale (continuous).
- Bayley-III *Language composite score*: Score based on conversion of combined Bayley-III receptive and expressive communication scaled scores (continuous).
- Bayley-III *Fine motor score*: Z-score converted raw score of Bayley-III fine motor subscale (continuous).
- Bayley-III *Gross motor score*: Z-score converted raw score of Bayley-III gross motor subscale (continuous).
- Bayley-III *Motor composite score*: Score based on conversion of combined Bayley-III fine and gross motor scaled scores (continuous).

We will use Bayley-III raw scores generated from each subscale based on the number of items passed and convert them into a z-score. Raw scores will also be converted into scaled scores based on normative data; the scale scores will be used to calculate cognitive, language and motor composite scores.

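### Does the SAP leave open whether any Bayley-III analysis adjusts for the assessor?

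*SAP*

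**What the plan says.** SAP section 5.1.2 screens covariates for each outcome by a bivariate likelihood ratio test: "Covariates with a p-value < 0.1 will be included in the adjusted analysis". The list that follows has 18 items. The last, and the only one tied to a single instrument, is "Staff members performing the assessment (for Bayley-III".

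Two adjusted models are then defined. For the baseline adjusted model, "This model will include covariates in minimally adjusted model and any of the following baseline covariates that are significantly associated" with the outcome; 14 covariates are named and the assessor is not one of them. For the fully adjusted model, "we will adjust for any covariates collected at follow-up (HOME inventory score, screen time") under the same p<0.1 condition. A further rule covers variables measured later: "For any covariates collected after baseline, we will check whether any differences are based on allocation groups" at p<0.1, and "Significant differences indicate potential mediators. Therefore, we will exclude them from the model".

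Section 2.7.2 explains why the assessor might matter. Two psychologists gave the test, and before the study "we evaluated inter-rater agreement between the two assessors using data from three children, which resulted in a 56% agreement rate". The disagreements were then discussed, but "we were unable to conduct additional inter-rater reliability assessments".

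Section 5.1 fixes the primary model for every outcome: allocation, child age and the two stratification factors. It describes the adjusted models as secondary and says they draw on baseline, post-enrollment and follow-up variables. Section 2.4 states that outcome assessors were blinded.

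**The concern.** The plan singles out a covariate for Bayley-III and then gives it no stated place. Three readings can be drawn from section 5.1.2:

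1. The model lists are closed, and the assessor enters no model.
2. The general p<0.1 rule admits the assessor.
3. The assessor counts as a post-baseline variable. It must pass the p<0.1 screen and is then removed as a possible mediator if it differs by arm at p<0.1.

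The third reading looks the most awkward. With blinded assessors a difference between arms is not mediation, and the rule would drop the term exactly when the arms are least balanced on it.

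Eight Bayley-III outcomes would be affected: two primary and six secondary, since the secondary outcomes follow the same approach. With 56% agreement in three children and no repeat check, a systematic difference between the two psychologists cannot be excluded. At stake would be the reproducibility of the adjusted estimates and some precision.

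**Working it through.** **Comparing the lists.** The 18 potential covariates in section 5.1.2 were set against the three models.

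- Two are in the minimally adjusted model (maternal education, municipality economic status).
- Twelve are among the 14 named for the baseline adjusted model.
- Two are named for the fully adjusted model (HOME score, screen time).
- 18 − 2 − 12 − 2 = 2 are in no model: the Bayley-III assessor and maternal history of hypertension.
- 14 − 12 = 2 are in the baseline adjusted model but not on the list: paternal age and paternal education.

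So the omission of the assessor is one of four mismatches between two lists that were not reconciled. It does not look like a decision about the assessor.

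**The plan's own sample size.** Section 2.6 uses 0.40 SD, two-sided alpha 0.05, 80% power and 33.3% attrition. By the normal approximation, n per arm = 2 × (1.96 + 0.84)² / 0.40² ≈ 98, taken as 99 before rounding of the quantiles. That is 198 in total, and 198 / (1 − 0.333) ≈ 297, in line with the stated 300. Conversely, 300 × (1 − 0.333) ≈ 200 analysed, or 100 per arm.

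**What the assessor term could add.** The SAP gives neither the size of a rater shift nor the split of children between assessors. Assumptions: an even split, 100 per arm, and a shift s of 0, 0.3 or 0.5 within-rater SD. The variance due to rater is v = s² × 0.25, relative to a within-rater variance of 1. Adjusting divides the standard error by √(1 + v). Power is for 0.40 total SD with a two-sided t-test.

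| s | v | Power without assessor | Power with assessor | Gain (points) |
|---|---|---|---|---|
| 0 | 0 | 80.4% | 80.4% | 0 |
| 0.3 | 0.0225 | 80.4% | 81.2% | 0.9 |
| 0.5 | 0.0625 | 80.4% | 82.7% | 2.3 |

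If the assessor is correlated with municipality economic status, which every model already contains, part of this is captured anyway. For s = 0.3 and 0.5 the gain is 0.6 and 1.7 points at a correlation of 0.5, 0.3 and 0.8 points at 0.8, and nil if the two coincide.

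**How far the readings diverge.** Simulated trials with no treatment effect, same assumptions:

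| s | Passes p<0.1 entry screen | Differs by arm at p<0.1 | Enters and is not excluded |
|---|---|---|---|
| 0 | 10% | 10% | 9% |
| 0.3 | 68% | 10% to 11% | 61% |
| 0.5 | 97% | 11% | 87% |

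Readings 2 and 3 share the same entry screen. They part only when the arm comparison fires, which is about the nominal 10% of that test. In those trials, leaving the assessor out moves the estimate by a mean absolute 0.04 SD (s = 0.3) or 0.07 SD (s = 0.5), with a signed mean of zero. The standard error of the difference is √(2/100) = 0.14 SD, so this is roughly 0.3 to 0.5 of one standard error. Without the assessor, the overall two-sided rejection rate under the null was 4.7% and 5.1% for the two shifts, so type I error is held.

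**The case for a change.** The strongest case for a change is about reproducibility. A prespecified model should be the same whoever fits it, and here it need not be. The general p<0.1 rule does not say which adjusted model receives the assessor, the bracketed follow-up variables are not marked as examples, and the mediator rule fits badly with blinded testers. Section 5.1 also says that secondary analyses will be done unblinded, so the choice could in principle be made with allocation known. A clarification would take about two lines.

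Much of that is true as a description of the text, but three things limit it.

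- The reading in which the assessor enters no model makes its place on the list pointless, so it is the least natural. The general rule governs the list that contains the assessor, and section 5.1 opens the secondary models to follow-up variables. An analyst would screen the assessor for Bayley-III outcomes and put it in the fully adjusted model. What stays open is narrow: whether it is also in the baseline adjusted model, and whether the arm-difference check applies.
- Blinding removes the route by which that choice could create bias. Even when the check fires, the effect is only that the secondary model, like the primary one, does not contain the assessor.
- The 56% agreement shows neither the size nor the direction of a rater shift, and it preceded the discussion of disagreements. A range that starts at 0.3 SD would overstate the case; zero belongs in it.

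Forcing the assessor into both adjusted models, exempt from the screen that other added covariates must pass, would be a preference and not the correction of an error.

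**Conclusion.** No change to the plan follows. The lists in section 5.1.2 do not match, for the assessor and for three other covariates, but this is a drafting gap in supportive analyses. The primary Bayley-III estimates come from a fully specified model and are the same under every reading. With randomised allocation and blinded assessors, all readings give an unbiased estimate, and the primary conclusion cannot depend on which is chosen.

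Under an assumed rater shift of 0 to 0.5 SD, an even split and 100 analysed per arm, the term is worth 0 to 2.3 points of power. It is worth less where the assessor follows municipality. That benchmark is the primary sample-size target, and the adjusted models have no power target to miss. The readings that screen the assessor differ from each other in about one trial in ten, by an amount well below one standard error. Analysts can be expected to settle the placement sensibly and report what they fitted. The conclusion would need another look only if assessors had not been blinded or if children had been assigned to them in a way related to allocation; the SAP gives no sign of either.

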Both groups consumed the supplements from the 2nd trimester of pregnancy until 6-months postpartum, regardless of their breastfeeding status. Omega-3 FAs supplementation began at 22 weeks of pregnancy, while probiotics/placebo supplementation started at 26 weeks. The gestational age for all subjects was assessed using ultrasonography at the nearest community health center or [name] General Hospital by trained general practitioners. These start times were chosen due to the late recognition of pregnancy in our population and therefore to ensure uniform initiation for all participants. Additionally, probiotics/placebo supplementation commenced during the third trimester because of limited evidence regarding probiotics use in pregnancy before this period. The placebo probiotics capsules were indistinguishable from the active capsules in appearance, taste, and odor. Likewise, the omega-3 capsules appeared identical across groups. All mothers in both groups also received psychosocial stimulation and healthy eating modules. These modules were delivered once during pregnancy (at 30–34 weeks of gestation) and twice during postpartum (between 0–1 month and between 1–2 months after birth). In the study sample, the majority of infants were breastfed, thus likely receiving DHA via their mother's breastmilk in addition to their prenatal exposure. Outcomes assessments were performed at 36–38 weeks of gestational age for fetal brain volume and when children reached the age of 4–6 months for Bayley-III, BERA, and eye-tracking assessments. All participants, outcome assessors, and field and research teams were blinded to the allocation of the intervention.

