### 2.7.1 Fetal brain MRI

Pregnant women were scanned in a supine position for fetal brain volume assessment on a 1.5-Tesla General Electric MRI with an acquisition time of approximately 30 minutes, depending on fetal motion. We used multi-planar repeated T2-weighted half Fourier acquisition single-shot turbo spin echo (T2wHASTE) sequences performed with a 2 or 4 interleaved acquisition; effective echo time of 100 and 120 ms; repetition time of 1400–2000 ms; variable field of view based on fetal and maternal size; 2–3 mm slice thickness; no inter-slice gap; 256×204, 256×256, or 320×320 acquisition matrices; and in-plane resolution of 1 mm.

Two independent trained physicians manually segmented brain regions of interest (i.e., whole brain, cerebrum, white matter, deep grey matter, cerebellum, and brainstem) with the supervision of a radiologist specialized in neurodevelopment; any discrepancies were reconciled with the radiologist. The outcomes derived from this assessment include:

- Whole brain volume in cm^3 (continuous).
- Cerebrum volume in cm^3 (continuous).
- White matter volume in cm^3 (continuous).
- Deep grey matter volume in cm^3 (continuous).
- Cerebellum volume in cm^3 (continuous).
- Brainstem volume in cm^3 (continuous).

Due to data quality issues, the myelination index could not be quantified as intended and was therefore excluded from further analysis.

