### 4.2. Baseline Characteristics

We will present characteristics of the study sample with continuous data as mean and SD or as median with 25th and 75th percentiles. Categorical variables will be presented as frequencies and percentages. We will indicate sample sizes for variables with more than 20% missing observations in the footnotes. Variables of the baseline characteristics are listed in **Table 1**, which best describe the study population, particularly in relation to child nutrition and cognition, as our predictor and outcome of interest in this analysis.

**Table 1.** Characteristics of the study sample

Variable	Definition
Baseline	
Child sex	2 categories: Female or male
Birth order	2 categories: First born or $\geq$ second-born
Municipality economic status	2 categories: High (Central and South Jakarta) or low (North and East Jakarta)
Maternal height	Maternal height in centimeters
Maternal pre-pregnancy BMI	BMI in kg/m 
Maternal hemoglobin level at baseline	Hemoglobin level in g/L
Maternal history of hypertension	2 categories: With a history of hypertension or without any history of hypertension
Maternal age	Maternal age in years
Maternal education	3 categories: No education/incomplete primary/unknown, Completed primary, Completed secondary or greater
Number of children	Number of children under 5 years old in the household
Number of household members	Total number of people in the household
Maternal marital status	3 categories: Monogamous marriage, polygamous marriage, or unmarried [single, divorced, widowed]
Maternal occupation	2 categories: Housewife or working mother
Paternal occupation	2 categories: Non-private sector and unemployed, or private sector
Monthly household expenditure	Household expenditure in Indonesian Rupiah per month
Endline	
Child age at outcome assessment	Child age in months (or gestational week for fetal brain outcome)
HOME inventory	HOME inventory score at the age of 4–6 months

Screen time	Screen time per day in minutes at the age of 4–6 months
-------------	---

HOME inventory, the Home Observation for Measurement of the Environment inventory.

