## SECONDARY OUTCOMES

### 5.1 Main Analysis

For all secondary outcomes, we will apply the same analytical approach used for the primary outcomes, including both the primary and secondary analyses. The primary analysis will use a minimally adjusted model, controlling only child age at assessment and the randomization stratification factors (maternal education and municipality economic status). In the secondary analyses, we will estimate adjusted parameters by adding additional covariates—baseline characteristics as well as post-enrollment and follow-up variables—in addition to those included in the primary analysis.

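### The secondary fully adjusted models and the HOME interaction can bring variables measured at 4–6 months of age into analyses of fetal brain volumes scanned before birth

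*SAP*

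**What the plan says.** **Timing.** SAP section 2.4 states: "Outcomes assessments were performed at 36–38 weeks of gestational age for fetal brain volume". Table 1 in section 4.2 places two variables under its endline heading: "HOME inventory score at the age of 4–6 months" and "Screen time per day in minutes at the age of 4–6 months".

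**Adjusted models.** Section 5.1.2 opens with "We will also perform baseline and fully adjusted analyses with covariates for each outcome". After the baseline adjusted model comes the fully adjusted one: "we will adjust for any covariates collected at follow-up (HOME inventory score, screen time"), where they are associated with the outcome at p<0.1. Follow-up covariates are also compared between arms at p<0.1: "Significant differences indicate potential mediators. Therefore, we will exclude them from the model".

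**Secondary outcomes.** The Main Analysis text under Secondary Outcomes says: "For all secondary outcomes, we will apply the same analytical approach used for the primary outcomes, including both the primary and secondary analyses". This brings in the regional fetal volumes. Section 2.7.1 names the segmented regions as "whole brain, cerebrum, white matter, deep grey matter, cerebellum, and brainstem".

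**Effect modification.** Section 5.3 tests the HOME score at 4–6 months against allocation for the primary outcomes. Table 2 lists fetal whole brain volume among them.

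**Primary analysis.** Section 5.1 and Table 2 adjust only for age at assessment (gestational age for the fetal scan) and the two stratification factors.

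**The concern.** The adjusted models and the HOME interaction are written once for a set of outcomes that spans birth. For the 4–6 month outcomes, HOME and screen time are roughly concurrent. For the fetal outcomes they come months later. An arm difference in fetal brain volume that has been adjusted for, or split by, the later home environment has no clear causal reading.

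The set of fetuses analysed would change as well. A model that contains HOME or screen time can use only fetuses whose child was also seen after birth. The minimally adjusted and fully adjusted columns for the same volume could then differ because of who is in them as well as what was adjusted for.

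**Working it through.** No figure in the SAP bears directly on this point, so the check is mainly one of time order against model scope.

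1. **Time order**

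| Item | When measured | Source |
|---|---|---|
| Fetal volumes | 36–38 weeks of gestation | 2.4, Table 2 |
| HOME score | 4–6 months of age | Table 1, 5.3 |
| Screen time | 4–6 months of age | Table 1 |

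2. **Is there an exemption for fetal outcomes?** None appears in 5.1.2, in 5.3 or under Secondary Outcomes. The SAP does restrict a covariate by outcome elsewhere: the assessor term in the 5.1.2 candidate list is marked as applying to Bayley-III. HOME and screen time carry no such mark.

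3. **Which fetal outcomes are reached?** Sections 2.1 and 2.2 together, and section 2.7.1, give six volumes: whole brain plus five regions. Tables 2 and 3 between them list five, because white matter is absent. The adjusted models reach all six if 2.7.1 governs. The HOME interaction reaches whole brain volume through 5.3 and Table 2. The secondary-outcome text rules out subgroup analyses, yet section 2.2 speaks of modification for every outcome, with home environment among the factors, and Table 3 lists whole brain volume a second time. The SAP therefore does not settle whether the interaction stops at whole brain volume.

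4. **Does the arm-difference screen help?** It asks whether allocation shifted HOME or screen time. A variable measured after the scan cannot lie on the path from treatment to the scan, so passing the screen does not justify its entry into a fetal model.

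5. **Could a postnatal covariate enter by chance?** Assume that HOME and screen time are unrelated to fetal volume, to allocation and to each other. For one volume, the chance that at least one is selected at p<0.1 is 1 − (1 − 0.1)² = 0.19. Requiring also that it pass the arm screen gives 1 − (1 − 0.1 × 0.9)² = 0.172. Entry is conditional but not remote. This says nothing about the size of any change in the estimate.

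6. **Can the change be sized?** Adding one covariate H to a least-squares model changes the treatment coefficient by exactly

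   adjusted = unadjusted − (slope of volume on H in the larger model) × (adjusted arm difference in H).

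   The SAP gives neither factor for HOME or screen time with any fetal volume. If the arms do not differ on H in expectation and H does not depend on fetal brain volume, the average change is zero.

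7. **Analysis set.** Section 3.5 takes complete cases to be everyone with the outcome recorded. A fetal model with HOME or screen time needs the outcome and the postnatal covariate. The SAP does not say how many scanned fetuses lack the latter.

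**The case against.** The strongest reply is that nothing confirmatory is touched. The minimally adjusted model is primary for every outcome, Table 2 defines every primary estimand by it, and section 5.1 calls the subgroup work unpowered and exploratory. That stands, and it limits the weight of the point. A reader might infer that the primary fetal result is biased; the documents do not support that.

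A second reply is that HOME at 4–6 months may stand in for a stable home environment that already existed in pregnancy. That is possible, but the SAP does not argue it. Its rationale in 5.3 is about children who may gain more from the intervention because they receive less stimulation at home. Maternal education, household expenditure and municipality are already available at baseline for that purpose.

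Other stronger readings should also be resisted:

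- **Attenuated fetal estimates.** This would need HOME to depend on fetal brain volume or on allocation. The SAP supplies no such link, and both arms received the same stimulation modules under blinding.
- **A stated loss of power.** The 33.3% attrition in section 2.6 underlies one sample size for the fetal and infant outcomes together. Taking a further loss off the sample that remains could count the same dropout twice.
- **No rule for missing covariates.** Complete-case analysis is stated in 3.5 and 5.1.1. The difficulty is only that 3.5 describes a wider set than these models can use.
- **A fault in the infant models.** Adjusting 4–6 month outcomes for HOME is a defensible trade-off. Section 5.1.2 does not claim that a non-significant arm difference rules out mediation.

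**Conclusion.** The point holds in a limited form. As written, the SAP allows fetal brain volumes to be adjusted for HOME and screen time recorded months later, and allows the effect on fetal whole brain volume to be examined by later HOME score. The p<0.1 arm screen does not cure this, and such models use a narrower set of fetuses than section 3.5 describes.

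The reach is up to six fetal volumes in the fully adjusted secondary models and, on the text of 5.3, whole brain volume in one exploratory interaction. Entry is not certain, because it depends on the p<0.1 rules. The effect on any fetal estimate cannot be sized from the SAP and may be nil. The conclusion rests on the timings in Table 1 and section 2.4 and on the absence of any exemption for fetal outcomes. It is worth correcting, but it gives no reason to doubt the primary analysis.

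**What to change.** In section 5.1.2 and under Secondary Outcomes, state that HOME and screen time are candidate covariates only for outcomes measured at 4–6 months. In section 5.3, restrict the HOME interaction in the same way. For all fetal volumes, use only baseline covariates and baseline modifiers. Name the six volumes explicitly, since Tables 2 and 3 omit white matter and a rule tied to those tables would miss it.

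The cost is SAP wording, plus the loss of the HOME- and screen-time-adjusted fetal results and the HOME-stratified whole brain volume result. No primary analysis changes.

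A separate editorial note, which adds no weight here: the covariate lists in 5.1.2 disagree. History of hypertension and Bayley assessor are candidates but appear in neither model's list. Paternal age and paternal education are in the baseline model's list but are neither candidates nor in Table 1. The lists should be made to agree.

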## 2.6. Sample Size

Sample size calculations were based on the hypothesized effect size of 0.40 standard deviation (SD) between intervention and control groups on fetal whole brain volume at 36–38 weeks of

gestational age, and on Bayley-III cognitive scores, BERA indicators, and eye-tracking assessment indicators at 4–6 months of age ( $\alpha=0.05$  and  $1-\beta=0.80$ ). The original protocol assumed an effect size of 0.30 SD and a 20% attrition rate, resulting in a minimum sample size of 400 participants. However, due to recruitment challenges and increased loss to follow-up during the COVID-19 pandemic, which raised the anticipated attrition rate to 33.3% and constrained available funding, a protocol amendment was made. The target sample size was revised to detect a difference of 0.40 SD between groups, generally considered moderate and likely to be of clinical importance, resulting in a lowered estimated minimum sample size from 400 to 300 participants. Effect sizes between 0.30 and 0.40 SD were chosen based on prior findings: for Bayley-III domains, Cohen's  $d$  values in developmental cohorts and preterm interventions fall within this range; neuroimaging studies show between-group brain volume differences of approximately 0.30–0.50 SD in fetuses and neonates; and intervention-related physiologic/eye-tracking changes are typically described in similar effect size terms.

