## 5. ANALYSIS OF THE PRIMARY OUTCOME(S)

### 5.1. Main Analysis

We will perform all analyses after the last participant in the follow-up study has completed their visit. We will review the characteristics of the study sample as blinded cohort. First, we will use fake IDs and scrambled group code to write the script for analysis and create dummy tables and figures. Once the script, tables, and figures are ready, we will insert the correct IDs with blinded group code (e.g., A vs. B) and create the draft of the interpretation of the results for each case (e.g., if “A” is the Control group vs. if “A” is the Intervention group). We will finally reveal the group assignments after all authors have reviewed and approved the results for the primary outcomes. Unblinded analyses will be performed for secondary analyses, such as effect modification and subgroup analyses.

For all outcomes, the primary analysis to answer each objective will be a minimally adjusted model controlling only for child age at assessment and the randomization stratification factors (maternal education and municipality economic status). In secondary analyses, we will estimate adjusted parameters by including additional covariates—baseline characteristics, as well as post-enrollment and follow-up variables—in addition to those included in the primary analyses.

Unless otherwise specified, we will use two-sided confidence intervals at the 0.05 significance level for all analyses. For example, we are not powered to conduct subgroup/effect-modification analyses, so these secondary objectives will be exploratory and considered significant at the  $\alpha=0.10$  level. All hypothesis testing in this analysis plan is based on a two-sided superiority framework.

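### In the secondary fully adjusted model, a p<0.1 arm-difference test is the only guard against adjusting for HOME score or screen time altered by treatment, and it misses about 58–59% of 0.2 SD shifts.

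*SAP*

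**What the plan says.** Section 5.1 (Main Analysis) fixes the primary result: "the primary analysis to answer each objective will be a minimally adjusted model", with age at assessment and the two stratification factors. For the secondary analyses, "we will estimate adjusted parameters by including additional covariates". These may be baseline characteristics or variables collected after enrolment.

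Section 5.1.2 splits the secondary analyses into a baseline-adjusted model and a fully adjusted model. For the fully adjusted model there are two steps, each at p<0.1:

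- Entry by association with the outcome: "we will adjust for any covariates collected at follow-up (HOME inventory score, screen time) that are significantly associated at" that level.
- Removal by arm difference: "we will check whether any differences are based on allocation groups at" that level. The consequence is: "Significant differences indicate potential mediators. Therefore, we will exclude them from the model".

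A follow-up covariate that passes the first step and does not differ significantly by arm therefore stays in. No subject-matter criterion for mediators is given. Table 1 lists HOME score and screen time as endline variables at 4–6 months. Section 2.4 starts omega-3 at 22 weeks of pregnancy and probiotics or placebo at 26 weeks. Section 3.10 adopts a treatment-policy estimand for all primary and secondary objectives. The Main Analysis section under Secondary Outcomes applies the same approach there.

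**The concern.** The treatment-policy effect is the total effect of assignment. Adjusting for a variable that assignment has changed removes the part of the effect that runs through that variable. The SAP recognises this, because it wants potential mediators out of the model. The weakness is the tool: a significance test by arm, in a trial not sized for it, decides whether a post-randomisation variable may be treated like a baseline covariate. If the test has little power for modest shifts, a variable that treatment did affect will often stay in. The fully adjusted estimate for an infant outcome then no longer targets the effect that section 3.10 says is being estimated.

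**Working it through.** **Inputs from the SAP.** Section 2.6: a "hypothesized effect size of 0.40 standard deviation (SD) between intervention and control groups", alpha 0.05, power 0.80, a minimum of 300 participants, and an amendment prompted by conditions that "raised the anticipated attrition rate to 33.3" per cent. Section 2.4: 157 randomised per arm. Section 5.1: "All hypothesis testing in this analysis plan is based on a two-sided superiority framework". Section 5.1.2: the p<0.1 threshold.

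**Inputs assumed.** The size of any arm shift in HOME score or screen time, and the slope of outcome on covariate (SD per SD). The SAP gives neither, so ranges are shown.

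**The plan's own sample size.** n per arm = 2(1.96 + 0.842)² / 0.40² = 98.1, rounded up to 99, so 198 in total. Dividing by (1 − 0.333) gives 297, which agrees with the stated 300.

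**Evaluable numbers.** 300 × 2/3 = 200, or 100 per arm. 314 × 2/3 = 209, or about 105 per arm. Both use anticipated, not observed, attrition.

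**Chance that the arm test misses a true shift d.** With δ = d / √(2/n), power = Φ(δ − 1.645) + Φ(−δ − 1.645), and the miss rate is 1 − power. For n = 100 and d = 0.20: δ = 0.20 / 0.1414 = 1.414, power = Φ(−0.231) + Φ(−3.059) = 0.41, miss rate 0.59.

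| Evaluable per arm | d = 0.10 | d = 0.20 | d = 0.30 |
|---|---|---|---|
| 75 | 84% | 66% | 42% |
| 100 | 82% | 59% | 32% |
| 105 | 81% | 58% | 30% |
| 157 (no attrition) | 77% | 45% | 16% |

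The miss rate is 50% at about d = 1.645 × √(2/n), which is 0.233 SD at 100 per arm and 0.227 SD at 105. The test misses more than half only below about 0.23 SD. For 80% power the shift must be about 0.35 SD at 100 per arm.

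**Effect of keeping an affected covariate.** Departure from the total effect = slope × shift. For a shift of 0.20 SD:

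- slope 0.2: 0.2 × 0.20 = 0.04 SD
- slope 0.3: 0.3 × 0.20 = 0.06 SD
- slope 0.4: 0.4 × 0.20 = 0.08 SD

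These are 10%, 15% and 20% of the 0.40 SD design effect. The standard error of a mean difference in SD units is √(2/100) = 0.141, or √(2/105) = 0.138.

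**Check by simulation of both steps** (20,000 trials, 100 per arm, total effect 0.40 SD, shift 0.20 SD). For slopes of 0.2, 0.3 and 0.4 the covariate passed the outcome-association step in 92%, 99.8% and 100% of trials. It ended in the model in 53%, 59% and 59%. In those trials the mean departure was −0.041, −0.059 and −0.080 SD, matching the arithmetic. Averaged over all trials, including those where it was removed, the departure was −0.012, −0.018 and −0.026 SD.

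**The case against.** Much can be said for leaving the plan alone.

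- *The main estimates are safe.* The primary estimand is the minimally adjusted difference, and section 5.1.2 already has a baseline-adjusted model without HOME score or screen time. The SAP attaches no decision to the fully adjusted model. This stands in full and limits the severity.
- *Mediation may be unlikely.* The arms differ in look-alike capsules under blinding, both received the psychosocial modules, and the SAP describes no route from the capsules to home environment or screen time. This stands as a reason to expect small shifts. Small shifts are also the ones the test cannot see, though they do less harm.
- *The rule limits its own damage.* A retained covariate has an observed imbalance below about 0.23 SD, so at slopes of 0.2–0.4 adjustment moves the estimate by less than about 0.05–0.09 SD, under one standard error. This stands, so the fully adjusted estimate is not uninterpretable.

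Two stronger readings are tempting, and the documents do not support them. A reader might infer that the rule also does harm by discarding an unaffected covariate in the 10% of trials with a large chance imbalance, and that changing the rule would cure this. It would not: without HOME score and screen time in the treatment-effect model, that imbalance is left uncorrected in every trial. It adds variance, not bias. A reader might also infer that the arm test makes the model differ from outcome to outcome. The comparison of HOME score or screen time by arm does not involve the outcome and varies only with which children have data. Differences between outcomes come mainly from the outcome-association step.

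**Conclusion.** The point holds, at minor severity. An arm-difference test at p<0.1 cannot establish that a variable measured after randomisation is unaffected by treatment. At 100–105 evaluable per arm it misses about 81–82%, 58–59% and 30–32% of shifts of 0.1, 0.2 and 0.3 SD. It would be wrong to say that it misses most mediators of any size.

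When an affected covariate with a 0.2 SD shift is kept, the estimate departs from the total effect by about 0.04–0.08 SD. That rests on assumed shifts and slopes and on the anticipated attrition. It is smaller than the standard error of about 0.14 SD, but unlike sampling error it does not average out. The consequence is confined to the fully adjusted estimates for infant outcomes. Nothing here touches the primary analysis or the baseline-adjusted model.

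**What to change.** In section 5.1.2, delete the arm-difference test as the rule for choosing covariates collected after baseline. State that the covariate-adjusted treatment effect is the one from the baseline-adjusted model already specified there. If models with HOME score or screen time are kept, label them descriptive and draw no treatment-effect conclusion from them. Align the wording in section 5.1 and in the Main Analysis section under Secondary Outcomes, both of which commit the secondary analyses to covariates collected after enrolment.

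The cost is rewording in three places, with no new data and no change to the primary analysis. One secondary model loses its status as a treatment-effect estimate. Chance imbalance in HOME score or screen time goes uncorrected, which costs some precision but introduces no bias.
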